6.4.2 Secondary Efficacy Variables

The secondary efficacy endpoints for this study are:

- Time to Progression (TTP) by RECIST v1.1, modified RECIST and EASL criteria
- Time to Worsening of PVT
- Time to Symptomatic Progression (TTSP)
- Tumor Response Rate (TRR), as objective response rate (ORR) and disease control rate (DCR) by RECIST v1.1, modified RECIST and EASL criteria
- Quality of Life (QoL) (FACT-Hep), including time to deterioration in QoL (TTDQoL)

6.4.2.1 Time to Progression

This secondary endpoint is TTP. TTP is defined as the time from date of randomization until date of radiological progression (including new liver lesions and extra-hepatic lesions) separately according to RECIST v 1.1, modified RECIST and EASL criteria assessed by investigator determination.

TTP (Months) = (Date of event/censor – Date of Randomization +1)/ 30.4375.

The censoring is performed in the following order:

- If a patient does not have a baseline tumor assessment, then the TTP time will be censored at the randomization date
- 2) If a patient is known not to have radiological disease progression, the TTP time will be censored at the date of death or at the last valid post baseline radiological tumor assessment date or at the randomization date if the patient does not have any post-baseline radiological tumor assessments.

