## 9.1.2.4 Q8 WEEKS FOLLOWING PROGRESSION TO DEATH

Every 8 weeks following determination of progression (Section 9.2.20), until death, a clinic visit or telephone follow-up (at the investigator's discretion, if a PS ≥ 2 (symptomatic progression) is assessed and whenever in the best interest of the patient) will be conducted. The following activities will take place:

- ECOG Performance Status (including date of death, if applicable) will be assessed as described in Section 9.2.6.
- 2. Record any treatment and concurrent medications to treat hepatocellular carcinoma and any adverse events as described in Sections 9.2.18, 9.2.19 and 12.3. Medications and therapies used in supportive care will not be recorded.
- 3. Patient Reported Outcome assessments will be obtained as described in Section 9.2.14 at clinic visits
- Child Pugh status will be assessed as described in Section 9.2.7

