## 9.2.17 Efficacy Imaging – CT/MRI

Baseline efficacy imaging scans will be obtained during screening and efficacy assessment scans will be taken every 8 weeks post randomization until progression is confirmed (see Section 9.2.20). Most patients will be evaluated by CT images. MRI images are also permitted. The imaging modality used at baseline must continue to be used for all efficacy images throughout the study. Triple phase CT will be used in accordance with site standards at baseline for dosimetry determination. SPECT imaging may be performed according to standard of care practices for clinical management but is not a study requirement.

Spiral CT abdomen/pelvis – must be performed with cuts of 10 mm or less in slice thickness contiguously in the axial plane. From these images, hepatic and extra-hepatic lesions will be read.

Spiral CT Chest – must be performed with cuts of 10 mm or less in slice thickness contiguously in the axial plane. From these images, extra-hepatic lesions will be read.

To enable analysis of secondary study endpoints using radiological assessment, investigators will identify, read and use bidimensional measurements of target lesions for size and will record evidence of enhancement and increase in dimension of a pre-existing thrombus for all image timepoints. These data will be captured on the eCRF. Comparison between baseline and subsequent images of quantitative and qualitative findings will determine response according to RECIST v 1.1, mRECIST and EASL which are assessed separately in secondary endpoint analyses.

Bone Scintigraphy – Bone scintigraphy to assess spread of metastatic disease will be performed according to institutional standards. For patients with AFP > 400 ng/mL at screening, results of bone scintigraphy will be recorded at the screening visit and subsequent study visits according to the site standard practice ( week 16 study visit and 6 months thereafter (i.e. months 10, 16, 22, etc.) ). Bone scintigraphy is suggested whenever there is an unjustified increase in AFP or the patient experiences bone pain or symptomatic deterioration and repeated at a frequency according to site standard practice.

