#### 9.2.20 DEFINITION OF PROGRESSION FOR PATIENT MANAGEMENT DECISION-MAKING

For the purposes of this trial, definition of clinical progression for patient management decisions will include assessment of change in PVT status and tumor progression and is defined as:

- Radiological progression as defined by RECIST v 1.1 (after receiving all allowable TheraSphere treatments as specified by the protocol)
  - And/OR
- Development of extra-hepatic disease beyond the limits defined in the eligibility criteria
- Worsening of PVT from baseline defined as change in classification of PVT (per Shi et al) up to Type Illa; Type IIIb or Type IV may not be retreated
- ECOG Performance Status ≥2

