5 CHANGES IN THE CONDUCT OF THE STUDY OR PLANNED ANALYSES

This SAP is based on protocol version 3.0 dated 08 August 2014. Due to challenges with patient recruitment the study was terminated prematurely; therefore, only a final analysis will be performed without any interim analyses..

Protocol section 10.2.3.2 states that time to progression (TTP) will be calculated as the interval between the randomization date and the date of first disease progression as defined by the respective criteria noted below, death for any cause or of last contact for patients alive. However, death will not be considered in the calculation of TTP. Section 6.4.2.1 of this SAP explains how TTP will be analyzed.

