6.4.2.2 Time to Worsening of PVT

Time to worsening of PVT is defined as the time from date of randomization until the date of any change in the classification of PVT type by at least one sub-type based on investigator assessment. Time to Worsening of PVT (Months) = (Date of event/censor – Date of Randomization +1)/ 30.4375.

The censoring is performed in the following order:

- If a patient does not have a baseline PVT classification, then the time to worsening of PVT will be censored at the randomization date;
- If a patient does not have a post baseline PVT classification, then the time to worsening of PVT will be censored at the randomization date;
- If a patient is known not to have worsening of PVT classification, the time will be censored at the last post baseline PVT assessment date.

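### Two secondary-endpoint censoring rules mishandle death: TTP may be censored at the death date after scans have stopped, and TTDQoL rule 2 drops deaths that are events

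*SAP*

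**What the plan says.** **TTP.** SAP 6.4.2.1 makes radiological progression the only event. Rule 2 opens with "If a patient is known not to have radiological disease progression" and then states that "the TTP time will be censored at the date of death or at the last valid post baseline radiological tumor assessment date", or at randomization if there is no post-baseline scan. The rules are applied in order, but that ranks rule 1 before rule 2; it does not rank the dates inside rule 2. SAP section 5, which departs from the protocol here, states that "death will not be considered in the calculation of TTP". For time to worsening of PVT, SAP 6.4.2.2 handles the same situation without a death date: "the time will be censored at the last post baseline PVT assessment date".

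**Imaging.** Protocol 9.2.17 says "efficacy assessment scans will be taken every 8 weeks post randomization until progression is confirmed (see Section 9.2.20"). Section 9.2.20 lists "Radiological progression as defined by RECIST v 1.1" but also non-radiological criteria, including "ECOG Performance Status ≥2". After that point, protocol 9.1.2.4 provides: "Every 8 weeks following determination of progression (Section 9.2.20), until death, a clinic visit or telephone follow-up". Its activity list contains no imaging. Protocol 9.1.3.5 is the same for the TheraSphere arm, except that retreated patients keep their scans.

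**TTDQoL.** SAP 6.4.2.5 and 8.9.2.5 define the event as a fall of at least 7 points in the FACT-Hep total or death, whichever is first. Rule 1 (no baseline form) censors at randomization and says that it does so even if the event was observed. Rule 2 (no post-baseline form) also censors at randomization and is silent on death. Under protocol 9.2.14, patients who cannot attend visits complete no form.

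**The concern.** A patient can meet the 9.2.20 definition through performance status, stop being scanned and die months later without RECIST progression. Rule 2 then offers two dates. If the programmer takes the death date, the patient stays in the TTP risk set through months when progression could not have been seen, and the Kaplan-Meier estimate is biased upward within that arm. TTP by mRECIST and EASL has a further gap, because scans may stop at RECIST v1.1 progression before those criteria are met.

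The bias need not cancel between arms, since it depends on when imaging stops and how long patients live afterwards. The trial is open-label and each TTP comparison is tested at 0.05, so the censoring date should not be left to a later choice.

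For TTDQoL, the patients caught by rule 2 include those who die or become too ill before the first form at Week 4. Read literally, the rule turns their deaths into censored times of one day.

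**Working it through.** The documents give no TTP or TTDQoL figure to reproduce, so the check applies the rules to worked patients and then sizes the effect under stated assumptions.

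**Worked patients**, using the SAP time formula (date − randomization + 1)/30.4375:

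- TTP, last clean scan at 56 days, death at 150 days: 57/30.4375 = 1.87 months by last scan; 151/30.4375 = 4.96 months by death date. The difference is 3.09 months.
- TTP, no post-baseline scan, death at 50 days: 1/30.4375 = 0.03 months by randomization; 51/30.4375 = 1.68 months by death date.
- TTDQoL, baseline form but no later form, death at 25 days: by definition an event at 26/30.4375 = 0.85 months; under rule 2 as written, censored at 0.03 months. The division by 30.4375 is applied here as for the other endpoints; the printed TTDQoL formula omits it although it is labelled in months.

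**TTP simulation** (200,000 patients per scenario):

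- *From the documents:* scans every 8 weeks; OS medians of 9 and 13 months (SAP 4.4); true TTP medians of 5.5, 2.8 and 7.9 months, taken from the sorafenib trials and the TheraSphere cohort described in protocol 5.3.
- *Assumed:* exponential progression, seen at the next scan if imaging still runs; exponential imaging end; exponential survival after imaging with median 2, 3 or 4 months. The imaging-end median is solved so that total OS keeps its median, giving 5.8/4.5/3.4 months for OS 9 and 9.9/8.3/6.9 months for OS 13. A share of patients is scanned until death. Patients alive at cut-off are censored at the last scan under both readings.

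For a true median of 5.5 months, the true progression-free proportion at 6 months (scans at weeks 8, 16 and 24) is 0.5^((168/30.4375)/5.5) = 49.9%. Last-scan censoring gives 49.5-50.1%. The excess from death-date censoring, in percentage points, is:

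| Share scanned until death | Follow-up 0-12 months | 0-24 months | Unlimited |
|---|---|---|---|
| None | 3.9-11.8 | 5.1-16.1 | 5.8-19.9 |
| Half | 2.0-5.4 | 2.6-8.0 | 3.1-10.2 |
| All | 0 | 0 | 0 |

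In these scenarios, roughly 40-68% of patients (none scanned until death) or 20-34% (half) stop imaging before progression would be seen. With half scanned until death and 0-24 months of follow-up, the excess is 3-11 points for a true median of 2.8 months and 2-6 for 7.9 months.

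**Between arms**, with equal true TTP, OS 9 versus 13 months, 0-24 months of follow-up and none scanned until death, the log-rank HR (longer-lived arm versus the other) is:

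- 0.93-0.97 if the arms differ only in survival after imaging;
- 1.12-1.34 if they differ only in when imaging stops;
- 1.00 with last-scan censoring.

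**TTDQoL.** With exponential OS of median m months, the fraction dying in d days is f = 1 − 2^(−(d/30.4375)/m). Removing those deaths at time 0 turns a deterioration-free proportion S into S/(1 − f). Take S = 35.5% at 6 months (assumed) and patients alive at day 14:

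- First form at day 28 (d = 14): f = 3.5% (m = 9) or 2.4% (m = 13); S becomes 36.8% or 36.4%.
- First form at day 42, the end of the Week 4 window in SAP 6.2.2 (d = 28): f = 6.8% or 4.8%; S becomes 38.1% or 37.3%.

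Over S = 20-50%, the shift is 0.5-1.8 points (day 28) or 1.0-3.7 points (day 42).

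**The case against.** **Section 5 defers to 6.4.2.1.** It can be read as saying only that death is not a TTP event, which is compatible with censoring at death. This is fair: section 5 does not by itself rule out the death date. It does not settle which date applies either, and the PVT rule shows that the SAP can state this cleanly.

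**TTDQoL is answered elsewhere.** SAP Appendix 2 says that patients without an event are censored, and rule 1 overrides observed events expressly while rule 2 does not, so rule 2 may be meant to leave deaths as events. That may be the intent, but a general programming line does not override a specific rule that sends every patient without a later form to randomization.

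**Imaging is less uniform than described.** Protocol 9.1.3.4 schedules treatment-arm scans every 8 weeks from randomization without the control arm's limit at progression. The radiological criterion in 9.2.20 applies only after all allowed TheraSphere treatments, and retreated patients keep being scanned. New lesions count as progression under all three criteria, which narrows the mRECIST and EASL gap; that gap is not sized here. These points stand. They make the size uncertain and possibly different by arm, but 9.2.17 still ends scans at 9.2.20 progression.

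**The sizes rest on assumptions.** This is true: the documents give neither imaging-end times nor survival after imaging, and the results start at zero. The 2.4% TTDQoL figure is also somewhat high for TheraSphere, because efficacy uses treated patients and treatment may come as late as week 4.

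**Last-scan censoring is not unbiased.** It also overestimates when imaging stops for reasons linked to imminent progression. That is correct, but the death-date rule adds further unscanned time to the same problem.

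**Conclusion.** The concern holds for both endpoints. TTP rule 2 permits a censoring date at which progression status is unknown and does not say when to use it. TTDQoL rule 2, as written, contradicts the endpoint's own definition for patients who die without a later form.

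If the death date is used, TTP within an arm is biased upward: by about 3-8 points at 6 months in the half-scanned, 0-24-month case, with a range from 0 to about 20 points over the 5.5-month scenarios. These are illustrations, not estimates. The direction between arms cannot be predicted. The TTDQoL effect is about 1 point, and up to 1.0-3.7 points with the later first form. Neither is a bound: patients who cannot attend have no form, while the eligibility requirement of more than 3 months' life expectancy may make early deaths rarer.

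The primary OS analysis is untouched. These are secondary endpoints in a trial that ended early, so the change should be made but is not critical.

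**What to change.** - **TTP (SAP 6.4.2.1, rule 2):** remove the death date. Censor every patient without radiological progression, dead or alive, at the last valid tumor assessment, or at randomization if there is none.
- **TTDQoL (SAP 6.4.2.5, rule 2):** apply the rule only to patients not known to have died, and count death as an event on its date.
- **TTSP (SAP 6.4.2.3), wording only:** rule 2 names only patients who never reached ECOG 2. Repeat the rule in protocol 10.2.3.2, so that anyone without confirmed symptomatic progression is censored at the last performance-status assessment. Counting an unconfirmed ECOG of 2 or worse followed by death as an event is at most an optional sensitivity analysis.

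The cost is two or three SAP sentences and the matching derivation code, with no new data. Some TTP times will be censored earlier, and TTDQoL will gain a few events.

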6.4.2.2 Time to Worsening of PVT

Time to worsening of PVT is defined as the time from date of randomization until the date of any change in the classification of PVT type by at least one sub-type based on investigator assessment. Time to Worsening of PVT (Months) = (Date of event/censor – Date of Randomization +1)/ 30.4375.

The censoring is performed in the following order:

- If a patient does not have a baseline PVT classification, then the time to worsening of PVT will be censored at the randomization date;
- If a patient does not have a post baseline PVT classification, then the time to worsening of PVT will be censored at the randomization date;
- If a patient is known not to have worsening of PVT classification, the time will be censored at the last post baseline PVT assessment date.

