# 1 PROTOCOL SYNOPSIS

Protocol Title	A prospective randomized clinical trial on  Yttrium trans-arterial radio-Embolization (TheraSphere®) vs. Standard of care (sorafenib) for the treatment of advanced Hepatocellular Carcinoma (HCC) with Portal Vein Thrombosis (PVT)							
Type of Protocol	Phase III protocol to collect efficacy and safety data							
Protocol Design	This is a two-arm, open-label, prospective, multi-center, randomized, active-controlled clinical trial.							
Study Objective	To assess efficacy and safety of TheraSphere in comparison to standard of care therapy (sorafenib) in the treatment of patients with portal vein thrombosis associated with unresectable hepatocellular carcinoma.							
Primary Endpoint	Overall Survival (OS) from time of randomization							
Secondary Endpoints	Time to progression (TTP) from time of randomization based on investigator assessment according to RECIST v 1.1							
	
 
Time to progression (TTP) from time of randomization based on investigator assessment according to modified RECIST
 
							
	Time to progression (TTP) from time of randomization based on investigator assessment according to EASL response criteria							
	Time to worsening of PVT from time of randomization to the time of any change in the classification of PVT type by at least one sub-type (see Section 9.2.5) based on investigator assessment							
	
 
Time to symptomatic progression (TTSP) from the time of randomization to assessment of ECOG performance status ≥2 with or without tumor progression based on imaging. Deterioration in performance status is to be confirmed at one subsequent evaluation 8 weeks later.
 
							
	Tumor response according to RECIST v 1.1 criteria based on investigator evaluations							
	
 
Tumor response according to modified RECIST criteria based on investigator evaluations
 
							
	
 
Tumor response according to EASL response criteria based on investigator evaluations
 
							
	
 
Patient reported outcome (PRO) as assessed by the Functional Assessment of Cancer Therapy – Hepatobiliary Questionnaire (FACT-Hep) questionnaire
 
							
	Adverse events (NCI-CTAE v 4.0)							
Trial Population	Patients diagnosed with portal vein thrombosis associated with unresectable advanced HCC, who are not eligible for any curative procedure.							

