#### 9.2.5 CLASSIFICATION OF PVT

The reference standard for characterizing PVT in cirrhotic patients with or without HCC is a histopathologic examination. However in the present trial for practical reasons, contrast enhanced CT scan or MRI and clinical and laboratory findings can be relied on for categorization of PVT adapted from Shi et al 2010^17 (see Appendix 2). Portal vein tumor thrombosis (PVTT) in HCC is defined as expansion of the thrombosis within the involved portal vein adjacent to the primary tumor and enhancement of the thrombus itself during the arterial phase on contrast enhanced CT or MRI. 

The mandatory requirements qualifying patients for the present study is the confirmation, according to standard criteria (histology or EASL/AASLD guidelines) of advanced stage HCC associated with branch PVT. For the purpose of this study, branch PVT is defined as Type Ia or Ib, Type IIa or IIb or Type IIIa as noted below. Presence of PVT in absence of focal liver lesions or associated only with high levels of AFP, is not eligible for the study because of the lack of a target lesion.

At the screening visit and subsequent Q8 weekly visits:

- venous location of the PVT will be recorded on the eCRF
- tumor location (lobe/segment) will be recorded on the eCRF
- PVT will be categorized based on dynamic imaging studies as:
  - Type I: segmental, to be demonstrated at imaging in at least one of the eight segmental branches of the portal vein (peripheral or sub-segmental venous invasion are not eligible)
  - Type II: branched (left or right branches of the portal vein)
  - Type III has been modified on the basis of extension of the tumor thrombus rather than on the length of the tumor thrombus; in particular:
    - Type IIIa, eligible to the study: thrombus involving the main portal trunk although allowing blood flow to the contralateral lobe (with no thrombosis)
    - Type IIIb, NOT eligible to the study: thrombus in the main portal trunk occluding blood flow to the contralateral lobe; includes portal cavernomas associated with main trunk thrombosis
  - Type IV: main PVT NOT eligible to the study; extended (mesenteric or splenic veins and/or sovra-hepatic veins)

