# **APPENDICES**

- 1. TheraSphere Product Labeling
  - a. US Package Insert http://www.therasphere.com/physicians-package-insert/package-insert-
  - b. CA Package Insert http://www.therasphere.com/physicians-package-insert/package-insert-ca.pdf
  - c. EU Instructions for Use http://www.therasphere.com/physicians-package-insert/package-insert-euen.pdfp (other languages are available at this website

[figure not shown]

Table 1 Classification of PVT

Classification of PVT	
Types	Subtypes
Type 1o: Tumor thrombi formation found under microscopy	
Type 1: Tumor thrombi involving segmental branches of portal vein or	Type Ia: Tumor thrombi involving segmental branches of portal vein or above
above	Type Ib: Tumor thrombi involving segmental branches of portal vein extending to sectoral branch
Type II: Tumor thrombi involving right/left portal vein	Type IIa: tumor thrombi involving right/left portal vein Type IIb: Tumor thrombi involving both left and right portal vein
Type III: Tumor thrombi involving the main portal trunk*	Type IIIa: Tumor thrombi involving the main portal vein trunk allowing blood flow to the contralateral lobe (with no thrombosis)  Type IIIb: Tumor thrombi involving the main portal vein trunk also occluding blood flow to the contralateral lobe (with no thrombosis)
Type IV: Tumor thrombi involving the superior mesenteric vein	

Note: patients with PVT classifications Type IIIb and Type IV noted above are not eligible under this protocol.

 $^{ullet}$ modified on the basis of extension of the tumor thrombus rather than on the length of the thrombus

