8.9.2.2 Time to Worsening of PVT

Time to worsening PVT rates will be derived and quartiles on the rates will be presented. 95% CIs will be calculated on the quartiles. A log-rank (two-sided) test will be used to compare time to worsening PVT between the two treatment groups at a 0.05 significance level. Plots of the Kaplan-Meier curves will be provided for each treatment group.

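### Two secondary endpoint derivations in the SAP are wrong as written: time to worsening of PVT has no direction, and time to deterioration in QoL has the wrong wording and lacks the months divisor

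*SAP*

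**What the plan says.** **PVT.** SAP 6.4.2.2 measures from randomization "until the date of any change in the classification of PVT type by at least one sub-type based on investigator assessment". The protocol synopsis has the same wording: "to the time of any change in the classification of PVT type by at least one sub-type". The third censoring rule in SAP 6.4.2.2 begins "If a patient is known not to have worsening of PVT classification" and censors such a patient at the last post-baseline PVT assessment. For the analysis, SAP 8.9.2.2 states: "A log-rank (two-sided) test will be used to compare time to worsening PVT between the two treatment groups at a 0.05 significance level". It also plans quartiles with confidence intervals and Kaplan-Meier plots.

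Protocol 9.2.5 has PVT categorized repeatedly ("At the screening visit and subsequent Q8 weekly visits") and sets the eligible range: "branch PVT is defined as Type Ia or Ib, Type IIa or IIb or Type IIIa as noted below". The sub-types themselves are described in the protocol's Appendix 2.

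**Quality of life.** SAP 6.4.2.5 puts the deterioration event (TTDQoL) at the assessment where the FACT-Hep total score has changed from baseline by 7 points or more, or at death if earlier. It states no order of subtraction, and the formula repeats the same condition. SAP 8.9.2.5 and protocol 10.2.3.2 both describe a 7-point decline (at least 7 points in the SAP) or death. SAP Appendix 4 says that higher scores mean better quality of life. The TTDQoL formula is labelled months but stops at the number of days plus one. The formulas for OS, TTP, PVT worsening and TTSP (SAP 6.4.1 and 6.4.2.1 to 6.4.2.3) all divide by 30.4375.

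**The concern.** Section 6.4 is where a programmer looks for derivations, and a literal reading of it gives the wrong events for two secondary endpoints.

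For PVT, a patient with regression only satisfies both the event definition and the censoring rule, so the section contradicts itself. A patient who regresses first and worsens later would have the event dated too early. For TTDQoL, the derivation section disagrees with the SAP's own analysis section about what the event is.

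The planned log-rank tests, quartiles and curves all depend on which patients count as events and when. SAP section 5 records that the trial was terminated early, and SAP 7.7 drops subgroups because few patients were enrolled. In a small data set, a handful of misclassified patients can move a quartile or a test result.

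**Working it through.** No design figure bears on this point, so there is no planned number to reproduce. The check compares passages and adds a unit conversion.

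**1. PVT: one patient under both rules.** Assume a patient who moves to a lower sub-type at day 56, stays there, and is last assessed at day 168. The SAP formula is (date − randomization date + 1)/30.4375.
- Event definition: event at (56 + 1)/30.4375 = 1.87 months.
- Third censoring rule: censored at (168 + 1)/30.4375 = 5.55 months.

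If the same patient were instead found worse than baseline at day 168, the literal event time would be 1.87 months and the directional one 5.55 months.

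**2. PVT: is an order stated?** Between main types the order is evident. Protocol 9.2.5 and Appendix 2 run from segmental branches to the right or left branch, the main trunk, and the veins beyond it, and both say that Type III was redefined by thrombus extent. Between sub-types it is not fully evident. Appendix 2 gives "Type IIb: Tumor thrombi involving both left and right portal vein", whereas IIIa reaches the main trunk but leaves the contralateral side free of thrombus. Neither contains the other, so a move between them cannot be coded as better or worse from the text. Appendix 2 also has no category for a thrombus that is no longer visible.

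**3. PVT: direction of the effect (assumed hazards only).** The documents give no rates of worsening or regression. The following constant monthly hazards are assumptions, with 12 months of follow-up. Worsening is 0.06 (TheraSphere) and 0.10 (control); regression r is added to give h. The median is ln 2/h. The expected log-rank Z is proportional to √(D/4) × |ln(h_T/h_C)|, where D is the sum over arms of 1 − exp(−12h).

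| r (TheraSphere / control) | h | Medians, months | Z relative to directional coding |
|---|---|---|---|
| 0 / 0 | 0.06 / 0.10 | 11.6 / 6.9 | 1.00 |
| 0.02 / 0.02 | 0.08 / 0.12 | 8.7 / 5.8 | 0.85 |
| 0.03 / 0.01 | 0.09 / 0.11 | 7.7 / 6.3 | 0.42 |
| 0.01 / 0.02 | 0.07 / 0.12 | 9.9 / 5.8 | 1.11 |

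For the second row, D = 0.617 + 0.763 = 1.380 against 1.212 with no regression. The ratio is √(1.380/1.212) × 0.405/0.511 = 0.85. The table shows only that the test can move in either direction; it does not estimate this trial.

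**4. TTDQoL: three readings of the event.** Higher scores are better.
- Follow-up minus baseline ≥ 7: counts a 7-point gain and misses a 7-point loss.
- Absolute change ≥ 7: counts both.
- Baseline minus follow-up ≥ 7: counts only the loss, and is the only reading that matches SAP 8.9.2.5 and protocol 10.2.3.2.

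**5. TTDQoL: units.** 365.25/12 = 30.4375 days per month. An event at day 168 comes out as 168 + 1 = 169 without the divisor and 169/30.4375 = 5.55 with it. The log-rank test and the Cox hazard ratio use only the ordering of times. On one simulated data set the log-rank chi-square was 0.4006 in both days and months.

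**The case against.** The strongest reply is that the intent is plain. The PVT endpoint is named for worsening, and the third censoring rule says the same. The deterioration endpoint is also named for its direction, and the SAP's analysis section and the protocol both state a decline. The missing divisor is an evident slip beside four formulas that carry it. Secondary tests in a trial stopped early, with no multiplicity adjustment (SAP 7.6), will not be read as confirmatory.

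Most of this stands, and it limits the point to a correction of wording. It does not make the text right. SAP 6.4.2.2 contradicts itself, SAP 6.4.2.5 contradicts SAP 8.9.2.5, and knowing that worsening is meant does not settle IIb against IIIa. The assumed hazards above come from no passage. They also leave the worsening hazard unchanged after a regression, although such a patient would first have to pass the baseline state again. They carry no weight on size.

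The patient-management definition in protocol 9.2.20 and the synopsis also uses loose wording ("Worsening of PVT from baseline defined as change in classification of PVT"). A reader might infer that it needs the same change. It serves a different purpose, and this correction does not extend to it.

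**Conclusion.** The definitions are wrong as written, for secondary endpoints only. Overall survival is untouched.

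- **PVT.** The event lacks a direction and conflicts with the section's own censoring rule, and the sub-type order is incomplete. The size of the effect cannot be derived from the documents. It is zero if no patient regresses, only an arm with regressors has its times shortened, and the log-rank test could move either way.
- **TTDQoL event.** The wording conflicts with the SAP's analysis section and the protocol. With change taken as follow-up minus baseline, it selects improvements.
- **TTDQoL units.** If programmed literally, quartiles, their confidence intervals and plot axes are 30.4375 times too large. The test and hazard ratio are unchanged.

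A reader might infer that the sponsor means to count regression or improvement as failure, or that a bias towards one arm is built in. The documents support neither: the names, the censoring rule and SAP 8.9.2.5 point the other way, and no passage gives a regression rate in either arm.

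**What to change.** 1. **SAP 6.4.2.2, with the same correction to the synopsis wording.** Define the event as the *first change to a more extensive PVT type or sub-type than baseline*. Add an explicit order of sub-types confirmed by the sponsor. The Appendix 2 listing order is the natural candidate, with the position of IIb relative to IIIa to be settled. Censor patients who are never worse than baseline (unchanged, regressed or resolved throughout) at their last PVT assessment. SAP section 5 already records a departure from the protocol for TTP and can record this one.
2. **SAP 6.4.2.5, text and formula.** Define the event as a *decrease from baseline of at least 7 points (follow-up minus baseline ≤ −7) or death, whichever occurs first*.
3. **SAP 6.4.2.5, formula.** Divide (date − randomization date + 1) by 30.4375.

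The cost is the wording of two definitions and one formula, plus the sponsor's confirmation of the order. No new data are needed and patients are not affected. If the derivations are already programmed, check which reading was coded.
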